15.3. Partner Testing

We will compare the following week 6 outcomes between the observation and intervention periods: (1) number of partners reported; (2) number of partners successfully contacted; (3) number of partners tested; (4) number of partners newly diagnosed with prevalent HIV

infection; (5) number of partners newly diagnosed with AHI (0 in the observation period); (6) number of HIV-infected partners newly engaged in care; (7) number of HIV-uninfected partners initiating PrEP. For PrEP cohort participants (intervention period only) we will also assess the proportion initiating PrEP by month 3 following cohort enrollment and the proportion with adherence >80%, measured by self-report or MEMS® cap at months 3 and 6 following PrEP initiation. The median, inter-quartile range, and range will be presented for each outcome in each period.

Outcomes will also be compared across study periods using Poisson GEE models with a small-sample variance correction [63]. Potential predictors, adjustment for confounding by calendar time, and interaction testing will be as described for the HIV-1 RNA testing intervention analysis above. We will also analyze local sexual network characteristics including the composition of individuals' personal sexual networks by attributes, relational type, relational timing, and relational duration. Characteristics will be compared for partners of index cases with AHI vs. prevalent HIV and for networks that include or do not include one or more AHI cases, using Pearson Chi square or Fisher exact tests for binary outcomes and non-parametric tests for continuous outcomes. We will also conduct a subset of these comparisons to the sexual networks of HIV-negative respondents provided through their CASI/CAPI data. Point estimates and standard errors for each behavioral parameter will be used to parametrize the modelling efforts described below. As above, in analyses in which multiple null hypotheses are tested, p values will be adjusted using the Holm–Bonferroni method.

15.4. Impact and Cost-Effectiveness

We will develop a stochastic, network-based model of HIV-1 transmission within the region. The general approach will follow that developed by [name] for modelling HIV-1 transmission among MSM in multiple international settings, including coastal Kenya [47], extended to a two-sex population. In essence, the model will simulate individuals distinguished by the following attributes: age, sex, sex of partners (males, females, both); sex worker status; circumcision status; HIV status; diagnosis status; time since infection; CD4 count; and treatment status, among possible relevant others revealed by our fieldwork. Individuals will be capable of undergoing any or all of the following transitions: enter the sexually active population; depart from the sexually active population; age; become infected; experience symptoms of AHI; become diagnosed; disclose HIV status to primary or secondary partners; change CD4 count; initiate treatment; change level of treatment adherence; cease treatment; experience opportunistic infections; or die.

Network dynamics will be modelled using the temporal exponential random graph model approach that [name] has co-developed [64]; this allows for complex dependences among relations to be modelled explicitly, in forms that preserve multiple features from observed data (e.g., proportion of males with concurrent partners, age mixing matrix) simultaneously. A range of partnership types is common in some parts of Eastern Africa, and likely maintains the persistence of transmission at observed levels, and the model will include these types. Our model will also explicitly include men who have sex with men only, women only, or both, given the epidemiological importance of all three populations in this area.

Population-specific birth and death rates, including general mortality and HIV survival trajectories, will be used to parameterize vital dynamics. Data on population structure will be drawn from the 2014 Kenya Demographic and Health Survey [65] and 2012 Kenya AIDS Indicator Survey [21], or more recent surveys when available. Existing rates of HIV testing,

treatment initiation, adherence, and disease progression and morbidity will be estimated from the latest available literature at the time of model-building. Parameters for sexual network modules will be derived from the partner testing and related network analysis. The impact of the HIV-1 RNA testing intervention and the enhanced aPS intervention on diagnosis and linkage to care for index cases and their partners will be estimated from study data; our model will then layer these onto the baseline model to estimate potential population-level impact. Sensitivity analyses will be conducted, especially around key parameters of the individual-level intervention impact. Model outcomes will include life-years lived with HIV or clinical AIDS, life-years lost, incident HIV cases averted, deaths averted, and DALYs averted. We will validate the HIV model using available Kenyan surveillance data [40].

The model will be used to predict the potential impact of our testing and aPS interventions on HIV incidence, disease progression, and mortality, with additional assessment of the value added by enhanced aPS for newly diagnosed patients with acute HIV infection. Five main scenarios will be modelled:

- 1. Baseline model (current guidelines and practice): no HIV-1 RNA testing, low use of PITC
- 2. Testing for acute and prevalent HIV infection with immediate linkage to care (intervention period)
- 3. Addition of enhanced aPS for newly diagnosed prevalent HIV infections (intervention period)
- 4. Addition of enhanced aPS for newly diagnosed acute HIV infections (intervention period)
- 5. Addition of PrEP provision to eligible partners tested through the enhanced aPS intervention (intervention period)

We will perform CEA from both the governmental (MoH) and societal perspectives. The governmental perspective includes only direct medical and non-medical costs that would be incurred by the Kenyan government if they implemented the intervention. The societal perspective includes all opportunity costs (i.e., medical costs from the governmental perspective plus costs incurred by patients for transportation and upkeep while seeking care, and costs of lost productivity while traveling to seek care, waiting in line, and seeking care). Costs will be divided into costs of the intervention and costs of HIV treatment. Costs of the intervention will be estimated separately for the HIV testing and enhanced aPS interventions. Direct medical costs of HIV testing will include costs of testing supplies, personnel, transportation, and communication. Costs of testing supplies are a factor of resource use for testing and unit costs obtained from local medical price lists. Costs of personnel are a factor of wages for clinical, laboratory, counselling, and field workers, and the time spent performing different activities. Time spent performing different activities, including partner tracing, will be obtained by conducting a primary time-and-motion surveys for HIV testing. Transportation cost for aPS will be estimated using the mean distance travelled and the travel cost per kilometer based on WHO Choice program data for Kenya [66]. Communication cost will be obtained by estimating the number of minutes per call, the mean number of calls, and costs per call-minute. Costs of HIV treatment include the costs of immediate ART during the intervention period, costs of other medications, and the projected lifetime costs of HIV treatment under different HIV testing and aPS scenarios. Indirect costs will be estimated using data from patient interviews and publically available data. Questions on patient transport costs, transport time, upkeep costs, and wages will be added to data collection forms. These will be combined with data on patient waiting and

Version 1.1 17 July 2018 Page **61** of **137**

patient contact time with health workers to estimate the indirect costs. For unemployed individuals, wages will be estimated based on Kenya's gross domestic product per capita.

We will combine effectiveness estimates from the HIV-1 RNA testing intervention, linkage to care, and aPS interventions with the cost estimates of each intervention to calculate cost per HIV-infected person identified and treated, and the incremental cost-effectiveness ratio (ICER) measured as cost per incident HIV case averted, cost per death averted, and cost per DALY averted. Disability weights for calculation of DALYs will be obtained from the latest global burden of disease study [67]. Following WHO guidelines, interventions will be judged to be cost-effective if the ICER is <3 times local GDP and very cost-effective if the ICER is <1 times local GDP per DALY averted [68]. Univariate and probabilistic sensitivity analyses will be performed to determine model robustness and the impact of varying different parameters through their plausible ranges on the estimate of cost-effectiveness.

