11.4. Assisted Partner Services (aPS)

- 11.4.1. Observation Period Participants Diagnosed with HIV Infection (Index Cases)
 - Standard HIV care guidelines in Kenya recommend testing of partners of the index case through passive partner referral. Patients diagnosed with HIV infection during the observation period will be encouraged to refer their partners for this testing.
 - Partner outcomes will be self-reported by these patients at the 6-week follow-up visit, after which all observation period index patients will be offered standard aPS (with research staff, instead of index cases, contacting named partners), using procedures summarized in section 11.4.2. Partner outcomes among observation period participants who agree to provide names for standard aPS will be documented by study staff as described below. Of note, testing of partners of index patients diagnosed in the observation period will not include the Xpert® HIV Qual test, but will consist solely of standard HIV rapid tests conducted according to Kenyan National Guidelines.
- 11.4.2. Intervention Period Participants Diagnosed with HIV Infection (Index Cases)
 - During the intervention period, we will administer our enhanced aPS intervention to all consenting index patients on the day of diagnosis, either at the health facility where the case was diagnosed or at the nearest KEMRI Research Clinic, depending on the patient's preference.
 - Research staff will describe the rationale for providing aPS and procedures for
 having providers immediately notify partners without directly revealing the index
 patient's identity. Specifically, staff will indicate that index patients who wish to
 inform partners themselves will be allowed up to 3 days to do so, after which
 research staff will notify partners following the aPS procedures. In addition, if an
 index patient requests that a certain partner not be contacted, the research team will
 respect the patient's wish and only contact partners for whom the index patient has
 given permission.
 - We will use an assessment form adapted from [name] completed aPS study
 to identify and exclude any individual from aPS who is determined to be at high risk
 of IPV, defined as reporting IPV within the last 1 month. Of note, partner notification
 following these eligibility criteria in [name] completed trial at VCT sites in
 Kenya showed no difference in IPV in the control and intervention arms.

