15. DATA ANALYSIS

15.1. HIV Testing Uptake and Diagnoses

We will compare the age and sex of individuals who accept vs. refuse screening, using Student t and Chi-square tests. In addition, we will tally reasons for refusal to participate among those eligible, and compare eligible individuals who refuse vs. consent to study enrolment, using Chi-square or Fisher exact tests for categorical variables and Student t tests or Mann-Whitney U tests for continuous variables. Proportions of individuals who accept screening, are determined eligible, and enroll will be presented, with exact binomial CI.

We will compare the proportion of patients with the following outcomes in the observation and intervention periods: (1) tested for HIV infection; (2) newly diagnosed with prevalent HIV infection (i.e., HIV seropositive); (3) newly diagnosed with AHI. Because we expect 0 AHI cases in the observation period, we will use a combined outcome (i.e., newly diagnosed acute or prevalent HIV-1) to model the effect of the intervention, so that models will converge. We will conduct analyses on the individual-level data, using log-binomial generalized estimating equation (GEE) models to account for clustering by health facility. We will use a small-sample variance correction to handle the small number of clusters [63]. Models will include indicator variables for calendar time period to control for trends in HIV incidence in the study area.

We will compare baseline characteristics between individuals in the observation and intervention groups, using Chi-square or Fisher exact tests for categorical variables and Student t tests or Mann-Whitney U tests for continuous variables. Where imbalances are identified, we will control for these potential confounders in secondary analyses using GEE models as above. We will also conduct exploratory analyses to identify predictors of the combined outcome (i.e., newly diagnosed acute or prevalent HIV-1) in the intervention group, including age, sex, marital status, symptom or symptoms reported, sex of partners, number of partners, condom use, transactional sex work, and other risk behaviors. We will test for interactions between the intervention and other variables such as sex, and will present stratified analyses if meaningful interaction is observed. In analyses in which multiple null hypotheses are tested, p values will be adjusted using the Holm–Bonferroni method.

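### Section 15.3 fits a Poisson GEE period effect to partner acute HIV infection, which is zero by design in the observation period, so no finite estimate exists; section 15.1's remedy is not carried over

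*Combined protocol and SAP*

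**What the plan says.** Section 15.3 opens with "We will compare the following week 6 outcomes between the observation and intervention periods: (1) number of partners reported" and goes on to seven outcomes. The fifth is the "number of partners newly diagnosed with AHI (0 in the observation period"), and the seventh counts uninfected partners who start PrEP. Medians, interquartile ranges and ranges are planned for each outcome in each period. The model sentence follows: "Outcomes will also be compared across study periods using Poisson GEE models with a small-sample variance correction". From section 15.1 it takes over the choice of predictors, the adjustment for calendar time and the interaction tests. It closes with "in analyses in which multiple null hypotheses are tested, p values will be adjusted using the" Holm–Bonferroni method.

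Section 15.1 faces the same zero among index participants and deals with it: "Because we expect 0 AHI cases in the observation period, we will use a combined outcome", with the stated aim of keeping the models estimable. It also says "Models will include indicator variables for calendar time period".

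Section 11.4.1 explains the zero among partners: "testing of partners of index patients diagnosed in the observation period will not include the Xpert® HIV Qual test". On timing, it says that partner outcomes are "self-reported by these patients at the 6-week follow-up visit, after which all observation period index patients will be offered standard aPS". Staff then document the partner outcomes of those who accept standard aPS.

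**The concern.** The partner AHI count is zero in one period because of the test used there, not by chance. A Poisson model with a period term has nothing finite to estimate in that case. Section 15.1 considered an explicit rule necessary for the same situation. Section 15.3 borrows three things from 15.1, and the combined outcome is not among them.

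Two things are at stake. First, a standard error and p value set by the stopping rule could enter the multiplicity adjustment and change the thresholds for the other partner outcomes. Second, standard aPS begins only after the week-6 data are taken. The week-6 ratio could therefore be misread as enhanced against standard aPS, or as the yield of RNA testing, in the report or in the inputs to section 15.4.

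**Working it through.** **Inputs.** Index cases: 28 in the observation period (2% of 1,375 = 27.5) and 75 in the intervention period (5% of 1,500), from the Protocol Summary. Observation-period partner AHI: 0, from 15.3 and 11.4.1. Intervention-period partner AHI, k: not given, so assumed and varied.

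**The plan's own figure.** Section 14 gives no figure for this comparison. Its nearest one, 39.8% to 56.3% for 48.0% of 150 partners, reproduces as the exact binomial interval for 72/150.

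**No finite estimate.** With a log link and independence working correlation, the intercept equation requires fitted and observed totals to agree over all index cases. The period equation requires the same over intervention index cases. Subtracting, the fitted means over the 28 observation index cases must sum to 0. Each fitted mean is exp(linear predictor) > 0, so no finite solution exists. Calendar indicators do not help: their equations also sum to the overall total, and the same subtraction applies.

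**What software returns.** The usual Poisson start is (y + overall mean)/2, so the zero group starts at k/206. Each iteration lowers its log mean by 1, while the other group settles at k/75. After m iterations the log ratio is m + log(206/75) = m + 1.01, whatever k is:

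| Iterations | Log rate ratio | Model-based p (k = 8 assumed) |
|---|---|---|
| 5 | 6.0 | 0.40 |
| 10 | 11.0 | 0.90 |
| 20 | 21.0 | 0.999 |

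The facility-clustered variance behaves differently (k = 8, Figure 2 layout, 6 facilities, t with 4 df):

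- Fits stopped at 8, 10 or 12 iterations: SE 0.42 to 0.82, and p < 0.001 in all 300 simulated data sets.
- Independence GEE at packaged defaults: log ratio about 23, SE between 22 and 290 across repeat runs, or undefined. A simpler layout with k = 3 gave log ratio 29, SE about 62,000, and an undefined bias-reduced variance.
- Exchangeable GEE (simpler layout, k = 3): undefined.

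**What the counts can say.** Given k events, all in the intervention period, the exact two-sided p against 75/103 is 1.0 for k = 2, 0.12 for k = 8 and 0.006 for k = 18. The lower exact 95% limit for the rate ratio is (28/75) × p/(1 − p) with p = 0.025^(1/k): 0.15 for k = 3, 0.44 for k = 6, 0.84 for k = 10. There is no upper limit.

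**Does the combined outcome work?** Assumed intervention yield per index case: 150 × 0.48 / 75 = 0.96 (section 14); 1.67 × 0.69 × 0.48 = 0.553 (section 6.4.4); or half of 0.553, because the 48% is not said to be new diagnoses. Dividing by the 3.22 ratio in 6.4.4 and multiplying by 28 gives 8.3, 4.8 and 2.4 expected observation-period diagnoses. The chance of none runs from exp(−8.35) = 0.0002 to exp(−2.40) = 0.09. In simulated trials with calendar indicators, the period effect was finite in 99.9%, 97.9% and 86.3%. At the lowest yield, a separate simulation had 13.6% non-finite fits; in 4.5 percentage points of these both periods had events, and the calendar indicators were the cause.

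**PrEP initiation.** Section 11.4.3 makes observation-period partners ineligible for the PrEP cohort, and 11.5 says PrEP is not then offered outside research in Kenya. It also expects wider availability and mentions other demonstration projects. The count is therefore expected at or near zero, not fixed at zero.

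**Timing.** Sections 11.2.2 and 11.4.1 both place the standard aPS offer after week-6 data collection. The observation-period figure at week 6 therefore reflects passive referral.

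**The case against.** The authors plainly know about the zero: 15.3 prints it beside the outcome, 15.1 shows they understand the convergence problem, and descriptive summaries are already planned. The model sentence does not say that every outcome is modelled. An omitted clause is a likely explanation. That stands as to intent, but the text makes no exception, and 15.1 judged a rule to be needed.

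A reader might infer that the analysis would produce a falsely significant AHI effect. The documents do not support that. The small standard errors arise only in fits stopped early by a rule the plan does not give. Packaged defaults return absurd or undefined output that an analyst would probably notice. The exact p of 0.12 rests on an assumed 8 events and is no benchmark.

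A reader might also infer that the partner comparison is invalid, or that the claim about enhanced against standard aPS in 6.3 and section 8 is an analytical error. The documents do not support that either. The Protocol Summary, 7.2 and 11.4.1 disclose the sequence. Outcome 4 still compares prevalent partner diagnoses by period. The week-6 contrast properly addresses the two-fold expectation against passive referral in section 8, and passive referral suits the current-practice baseline in 15.4. What remains is a matter of labelling.

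**Conclusion.** The rule in 15.3 fails as written for partner AHI. Non-existence of the period effect follows from the zero alone and needs no assumption about event numbers. The size of the harm is uncertain: it depends on software, the stopping rule and whether anyone accepts the output. PrEP initiation is likely to have the same problem, though its zero is expected, not structural. The matter concerns secondary endpoints and is worth correcting because the remedy is already in 15.1. The estimability figures for the combined outcome rest on the assumed yields and on the borrowed 3.22 ratio.

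**What to change.** - In 15.3, model newly diagnosed acute plus prevalent partner infections as one combined outcome, as in 15.1.
- Report partner AHI descriptively by period, with no fitted ratio and no p value in the Holm-Bonferroni set. Do the same for PrEP initiation if it has no observation-period event.
- If any other model lacks a finite period effect, whether from a zero count in one period or from the calendar indicators, give counts by period without a fitted ratio.
- Describe the week-6 contrast as enhanced aPS against passive referral. Do not present it, or its use in 15.4, as enhanced against standard aPS or as the yield of RNA testing. The standard-aPS outcomes that staff already document can be described beside the enhanced-aPS yields, without a formal test: 28 and 75 index cases would need a ratio of roughly 1.8 to 2.9 for 80% power at the assumed yields.
- Separately, reconcile Appendix 21.3 footnote 2 (rapid tests for intervention-period partners tested at home) with 11.4.3 and 12.1.3 (RNA testing for them too), because this decides who can be counted as partner AHI.

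The cost is SAP wording, a summary of data already collected and one footnote. One stated model is given up. The combined outcome does not isolate AHI and may be sparse in the observation period.

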 - Staff will then ask whether the patient (if eligible) accepts aPS, and have the patient
 provide written informed consent for the aPS procedures, which include the
 collection of detailed information on the aPS participant's recent sexual partners.
 - Prior to initiating aPS interviews, research staff will explain that all information collected through the aPS process will be kept confidential, and reminded that staff will not reveal index cases' identities when contacting their partners.
 - Index patients who accept aPS will be interviewed using structured interview forms
 that will be used to obtain partner contacts and track partner outcomes.

- Research staff will use a timeline-follow back instrument to elucidate the number of
 unique sex partners that participants have had in the past 1 year for prevalent
 infection and the past 3 months for AHI. If any participant reports injection drug
 use, information about needle-sharing partners will also be elicited.
- For each identified sex partner, staff will collect information including demographic characteristics, contact information, case's relationship to the partner, case's sexual behavior with the partner, and case's knowledge of the partner's HIV status. All data will be collected using structured interview forms and recorded as numerical or categorical outcomes.
- Index cases will be assigned unique identification (ID) numbers and their partners
 will be assigned corresponding numbers that include a random prefix (to protect
 index case confidentiality) and an additional sequential number for each partner,
 allowing partners to be linked to index cases in our dataset.
- aPS intervention participants who are assessed as having a moderate risk for IPV, as
 described in section 13.3.3 under "Rating System for IPV" will undergo special
 monitoring after the aPS consent visit, as described in that section.

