Accounting for correlation within sites (i.e., facilities participating in the randomized trial), precision for the estimated rate of AHI detection is ±0.54%, assuming a prevalence of 1% and k=0.25; if AHI prevalence is 2%, precision will be ±0.81%. For the evaluation of impact and cost-effectiveness, precision is more important than power, since estimates will be used as ranges for modelling. Assuming 150 partners tested as a result of the aPS intervention, we can estimate their HIV prevalence with reasonable precision (binomial confidence limits [CL], 39.8%–56.3%, for 48.0% prevalence); in addition, we will have 80% power to detect a relative risk (RR) of 1.58 or higher for HIV infection in the partners of AHI patients (n=30), compared to partners of prevalent HIV patients (n=120). Assuming 75 new HIV diagnoses from the HIV-1 RNA testing intervention to detect acute and prevalent HIV infection, we can estimate the proportion attaining virologic suppression with reasonable precision (binomial CL, 69.2%–88.3% if 80.0% achieve suppression by month 12); we will have 80% power to detect an RR of 2.84 or higher for failure to suppress among AHI patients (n=15) compared to prevalent HIV patients (n=60).

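### Section 15.3 tests partners of acute versus prevalent index cases as independent people although they are nested within index cases; section 14's partner HIV-infection figures also hold only under independence

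*Combined protocol and SAP*

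**What the plan says.** Section 15.3 (Partner Testing) sets out a network analysis: "Characteristics will be compared for partners of index cases with AHI vs. prevalent HIV and for networks that include or do not include" an acute case. The tests are given as "using Pearson Chi square or Fisher exact tests for binary outcomes and non-parametric tests for continuous outcomes". No term for the shared index case appears. A subset of these comparisons is also to be made with the networks reported by HIV-negative respondents. Point estimates and standard errors of the behavioural parameters then go to the transmission model.

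The Poisson GEE models in 15.3 compare study periods only. The one clustering level named for GEE, in 15.1, is the health facility. The Holm–Bonferroni adjustment deals with multiple tests, not with dependence.

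Section 14 gives two figures for a different outcome, HIV infection in partners. The first begins "Assuming 150 partners tested as a result of the aPS intervention" and reports "binomial confidence limits [CL], 39.8%–56.3%, for 48.0% prevalence". The second is "we will have 80% power to detect a relative risk (RR) of 1.58 or higher for HIV infection in the partners of AHI patients (n=30"); its reference group is the 120 tested partners whose index case has prevalent infection. The same paragraph expects 75 new diagnoses, 15 acute and 60 prevalent. It allows for correlation within sites, but only for the AHI detection rate.

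Section 11.4.2 has partner identifiers built from the index case's number, "allowing partners to be linked to index cases in our dataset".

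**The concern.** In the partner-level comparison the exposure is fixed by the index case, while the unit tested is the partner. Partners of one index case are likely to resemble each other in sex, relationship type and timing. A test that counts them as independent then overstates the information, most of all in the small acute group (about 15 index cases).

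What is at stake is the false-positive rate of these comparisons. It also matters for any partner-level standard errors passed to the transmission model, because section 14 says that precision matters more than power there. As a separate matter, a reader of section 14 cannot tell that its partner interval and power assume no correlation within index cases.

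**Working it through.** **Inputs.** From section 14: 150 partners tested (30 and 120), 75 index cases (15 and 60), partner HIV prevalence 48%, RR 1.58. Mean cluster size m = 150/75 = 30/15 = 120/60 = 2. Alpha is 0.05, with two-sided testing assumed. The ICC is not given, so a range is used. Cluster sizes are assumed either fixed at 2 or 1 + Poisson(1) (mean 2, variance 1, CV 0.5).

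**Step 1: reproduce section 14 under independence.**
- The exact binomial interval for 72/150 is 39.8%–56.3%, as stated.
- Power: p₀ = 0.48 and p₁ = 0.48 × 1.58 = 0.7584, so the difference is 0.2784. The pooled p = (30 × 0.7584 + 120 × 0.48)/150 = 0.5357. SE₀ = √[0.5357 × 0.4643 × (1/30 + 1/120)] = 0.1018. SE₁ = √[0.7584 × 0.2416/30 + 0.48 × 0.52/120] = 0.0905. z = (0.2784 − 1.96 × 0.1018)/0.0905 = 0.87, giving 80.8%. The RR detectable at 80% power is 1.575.

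Both figures match, so neither contains an allowance for shared index cases.

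**Step 2: false-positive rate of the tests named in 15.3.** Beta-binomial simulation, 20,000 runs per setting, 15 versus 60 index cases, true proportion 48% in both groups, nominal 5%:

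| ICC | Chi-square, fixed 2 | Chi-square, 1+Poisson(1) | Fisher, fixed 2 | Fisher, 1+Poisson(1) |
|---|---|---|---|---|
| 0 | 5.1% | 4.9% | 3.8% | 3.8% |
| 0.1 | 6.5% | 6.7% | 5.0% | 5.3% |
| 0.2 | 7.5% | 8.5% | 5.8% | 6.8% |
| 0.3 | 9.0% | 10.3% | 7.3% | 8.5% |
| 0.5 | 11.3% | 13.4% | 9.2% | 11.4% |

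The approximation 2 × [1 − Φ(1.96/√DE)], with DE as in step 3, agrees: 6.2–6.8% at ICC 0.1, 8.6–10.4% at 0.3 and 11.0–13.8% at 0.5.

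**Step 3: section 14's partner HIV-infection figures with correlation.** DE = 1 + [m(1 + CV²) − 1] × ICC, which is 1 + ICC for fixed clusters of 2 and 1 + 1.5 × ICC for 1 + Poisson(1). Both standard errors in step 1 are multiplied by √DE. Each cell gives fixed 2, then 1 + Poisson(1):

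| ICC | DE | Effective n | 95% interval | Power at RR 1.58 | RR detectable at 80% power |
|---|---|---|---|---|---|
| 0.1 | 1.10; 1.15 | 136; 130 | 39.4–56.7%; 39.2–56.9% | 77%; 75% | 1.60; 1.61 |
| 0.3 | 1.30; 1.45 | 115; 103 | 38.6–57.5%; 38.1–58.0% | 69%; 64% | 1.65; 1.68 |

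These are powers for a test whose size has been restored to 5%. The unadjusted chi-square would still reject in about 77–79% of runs at ICC 0.3, but with a false-positive rate of 9–10%.

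The sign matters. At ICC −0.1 with fixed pairs, DE = 0.9 and z = (0.2784 − 1.96 × 0.1018 × √0.9)/(0.0905 × √0.9) = 1.04, giving power of about 85%. The stated figures would then be conservative.

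**Sensitivity to cluster size.** With m = 1.67, the number of partners named per index case in the earlier Kenyan trial (section 6.4.4), power at ICC 0.3 is 73% for equal clusters and 68% at CV 0.5.

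**The case against.** Several points on the other side stand.

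- A reader might infer that the network comparison has its own stated power and that this power is overstated. It does not. The RR 1.58 and the 39.8%–56.3% interval concern partner HIV infection. No power is stated for network characteristics, and 15.3 names no separate test of partner infection by index-case status. The two issues share a cause but are distinct.
- A reader might infer that the section 14 figures are certainly too favourable. Without an ICC that cannot be said. If typically one partner is the source of an index infection, HIV status among partners of that index case could be negatively correlated.
- Section 15.3 also describes personal networks and compares networks with and without an acute case. One record per network has no nesting of partners.
- Rates of 17–22% arise at ICC 1, for traits fixed entirely by the index case. The text does not say that such traits would be tested once per partner, so these rates should not be the headline.
- At low ICC the inflation is small, and Fisher's conservatism absorbs it up to about 0.1.
- The mean of 2 is inferred from 150/75. The earlier trial enrolled fewer partners per index case (1,292/1,119 = 1.15, counting index cases with none). Newly diagnosed partners also become index cases, so 150 partners could come from more than 75.
- Section 15.3 does not say how the standard errors for the model are computed, and sensitivity analyses are planned. Harm to the model results is possible but not shown.

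None of this supplies a method that respects the nesting for the partner-level tests.

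**Conclusion.** The point holds for partner-level comparisons by index-case status. As written, the chi-square test has a false-positive rate of about 6–7% at ICC 0.1, 9–10% at 0.3 and 11–14% at 0.5 for positively correlated traits. This assumes 15 versus 60 index cases and a mean of 2 partners each. Section 14's partner interval and power are correct arithmetic under an unstated independence assumption. With positive correlation, power is 75–77% at ICC 0.1 and 64–69% at 0.3; with negative correlation the figures are conservative.

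No primary or secondary endpoint test is affected. The primary analysis, the sample size of 2,875 and the period comparisons by GEE stand. This is a contained correction to a supporting analysis and does not threaten the trial's main conclusion.

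**What to change.** **Section 15.3.** State the unit of analysis for each network comparison. Where it is the partner, cluster on the index case, or on the aPS chain where partners of partners are included. Use a GEE or robust-variance model with a small-sample correction, since only about 15 index cases are acute. Alternatively, permute acute/prevalent status across index cases. Apply the same clustering to comparisons with HIV-negative respondents' partners, because section 11.2.1 collects detail on up to three partners per respondent, and to any partner-level standard errors passed to the transmission model.

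**Section 14.** State that the partner interval and the RR 1.58 power assume independence, and give both over a stated ICC range, for example 0.05–0.3, noting that a negative correlation would work the other way.

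**Cost.** Some SAP wording and a few lines of code. The index–partner link is already recorded, so no new data or participants are needed. The downside is slightly less favourable stated precision and power.
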